# 3. STUDY DESIGN AND RATIONALE

JNJ-63723283 given in combination with daratumumab

versus daratumumab alone (Part 3 only)

# 3.1. Overview of Study Design

This is a randomized, open-label, multicenter, multiphase study assessing the efficacy and safety of JNJ-63723283 (an anti-PD-1 monoclonal antibody) in combination with daratumumab compared with daratumumab alone in subjects with multiple myeloma who have received at least 3 prior lines of therapy including a PI and an IMiD or whose disease is double refractory to both a PI and an IMiD.

A diagram of the study design is provided in Figure 1.

Clinical Protocol 54767414MMY2036 Amendment 2

#### Figure 1: Study Scheme

## Part 1: Safety Run-in Phase

A 6-subject Safety Run-in cohort will be evaluated by the Safety Evaluation Team (SET; see Section 3.2) to determine the safety and tolerability of JNJ-63723283 in combination with daratumumab before the start of the randomized phase of Part 2 of the study. The DLT evaluation period for the Safety Run-in cohort will be 1 cycle (28-days).

- Study drug administration:
  - Daratumumab: Daratumumab 16 mg/kg IV will be administered once every week (Weeks 1 to 8); then once every other week for 16 weeks (Weeks 9 to 24); then once every 4 weeks (Week 25 onwards).
  - JNJ-63723283: 240 mg IV (fixed dose) will be administered during Week 1 on Cycle 1 Day 2, Cycle 1 Day 15, then every 2 weeks thereafter.
  - Daratumumab will be administered prior to administration of JNJ-63723283. Subjects will continue to receive study treatment until confirmed disease progression, unacceptable toxicity, or any other treatment discontinuation criteria are met.
- If <2 of the first 6 DLT evaluable subjects experience a dose-limiting toxicity (DLT; see Section 3.2) during the first treatment cycle (ie, 28 days), the selected doses and dose regimens for JNJ-63723283+daratumumab combination therapy will be considered tolerable, and the study will proceed to the Part 2 randomized phase after the SET provides approval.
- If ≥2 subjects experience a DLT during the first treatment cycle (ie, 28 days), new subject enrollment into the Safety Run-in cohort will stop until after the SET convenes to review DLT data from those subjects and makes recommendations regarding the conduct of the study. The SET may consider the exploration of alternate doses and dose regimens, in an additional safety run-in cohort.
- Subjects in the Safety Run-in cohort may continue to receive additional cycles of JNJ-63723283+daratumumab while enrollment into the Safety Run-in cohort is ongoing and after the study has proceeded to the randomized phase until they meet protocol-specified discontinuation criteria. Subjects who experience unacceptable toxicity directly attributable to JNJ-63723283 may be eligible to receive daratumumab alone, after consultation with the Sponsor.

# Part 2 (Phase 2) and Part 3 (Phase 3)

Subjects will be assigned randomly in a 1:1 ratio into 2 treatment arms as indicated in Table 3.

	Planned Number of Subjects	
Study Arm	Part 2	Part 3
Arm A: daratumumab	40	150
Arm B: JNJ-63723283 + daratumumab	40	150

#### Table 3:Subject Randomization

# Treatment (Part 2 and Part 3)

Treatment cycles will be 28 days in duration.

- Daratumumab: Daratumumab 16 mg/kg will be administered IV once every week (Weeks 1 to 8); then once every other week for 16 weeks (Weeks 9 to 24); then once every 4 weeks (Week 25 onwards).
- JNJ-63723283: For Arm B, JNJ-63723283 240 mg IV (fixed dose) will be administered during Week 1 on Cycle 1 Day 2, Cycle 1 Day 15, then every 2 weeks thereafter. Daratumumab will be administered prior to administration of JNJ-63723283, when they are administered on the same dosing days.

Subjects will continue receiving the assigned study treatment (daratumumab or JNJ-63723283+daratumumab) until treatment discontinuation due to disease progression, unacceptable toxicity, or other protocol-defined treatment discontinuation criteria are met (see Section 10). Subjects in Arm B, who experience unacceptable toxicity directly attributable to JNJ-63723283 and who are experiencing clinical benefit (ie, stable disease or better) may stay on daratumumab until treatment discontinuation criteria are met, after discussion with the Sponsor. After disease progression is documented, survival status, subsequent anticancer treatment, and response to subsequent anticancer treatment will be recorded for all subjects until study end. The end of the study is defined in Section 17.9.1. Study evaluations (eg, disease assessments) are described in Section 9. The timing of study assessments is provided in the Time and Events Schedules (Table 1 and Table 2).

## **Initiation of Part 3 (Phase 3)**

After all 80 randomized subjects in Part 2 (Phase 2) have been followed for approximately 4 months or discontinued earlier, the Sponsor will determine whether the Part 2 primary efficacy endpoint was met and if the combination of the 2 drugs is safe. In addition, the secondary endpoint results, as well as all other available data, will be examined and taken into consideration. Based on the totality of the data, the Sponsor will decide whether Part 3 (Phase 3) will be initiated. This decision will be made in consultation with health authorities and the final decision will be communicated in writing to sites and independent ethics committees (IECs)/institutional review boards (IRBs), as appropriate.

If Part 3 is initiated, after the primary efficacy analysis, subjects remaining in the study will continue to be followed up until 205 deaths have occurred in this part.

# **Overall Design for Daratumumab Monotherapy Period**

As of 25 May 2018, the Sponsor terminated further enrollment into this study, 54767414MMY2036. In addition to discontinuing enrollment into this study, treatment with the combination of daratumumab and JNJ-63723283 will be discontinued and ongoing subjects will be given the option to continue on daratumumab monotherapy.

In the Daratumumab Monotherapy Period, each cycle is 28 days, and administration of daratumumab is to occur weekly for Cycles 1 and 2, every other week for Cycles 3 to 6, and

every 4 weeks for Cycles 7 and onwards until disease progression, pregnancy, unacceptable toxicity, loss of follow-up, withdrawal of consent, or death. Scheduled assessments to be performed during the daratumumab monotherapy period for subjects no longer receiving JNJ-63723283 in combination with daratumumab are outlined in the Time and Events Schedule in Attachment 11 / Table 24.

# 3.2. Safety Evaluation

# **Dose-Limiting Toxicity (DLT) Evaluation - Safety Run-in**

Toxicities will be graded for severity according to the National Cancer Institute Common Terminology Criteria for Adverse Events (NCI-CTCAE), Version 4.03. During the 6-subject Safety Run-in phase, the DLT evaluation period is 28 days starting from the day of the first dose of study drug. Only toxicities that occur during the DLT evaluation period will be considered for DLT assessment. A subject who received  $\leq$ 75% of a planned dose without experiencing a DLT may be replaced.

Dose-limiting toxicity is defined as any of the events listed in Table 4. Toxicities with a clear alternative explanation (eg, due to disease progression) or transient toxicities ( $\leq$ 72 hours) and abnormal laboratory values without associated clinically significant signs or symptoms based on investigator determination can be deemed a non-DLT.

	e mining rowery	
DLT criteria for Non-hematologic Toxicity a		
AST or ALT	Grade $\geq$ 3 persisting $\geq$ 7 days after treatment with corticosteroids, Grade 4, or any case meeting Hy's Law criteria b	
Laboratory abnormality	Grade 3 persisting $\geq$ 7 days despite BSC c or Grade 4	
Any other	Grade 3 persisting $\geq$ 7 days despite BSC c or Grade 4; except Grade $\geq$ 3 asymptomatic or mildly symptomatic rash that can be adequately managed with supportive care or resolves to become asymptomatic or Grade $\leq$ 2 within 7 days of supportive therapy.	
Infusion-related reaction	Grade 4 infusion-related reaction that occurs during or within 24 hours after the infusion of JNJ-63723283 or daratumumab.	
DLT criteria for Hematologic	Toxicity a	
Neutropenia	Grade 4 neutropenia lasting more than 7 days despite BSC c , or Grade 3 febrile neutropenia (ANC <1000 cells/mm  and a single temperature >38.3°C or a sustained temperature >38°C for >1 hour), or sepsis	
Thrombocytopenia	Grade $\geq$ 3 thrombocytopenia with clinically significant bleeding and Grade 4 thrombocytopenia lasting more than 7 days despite BSC c	
Anemia	Grade 4 for more than 7 days despite BSC c	
DLT criteria for both Non-hematologic and Hematologic Toxicity a		
Any Grade 5 non-hematologic or hematologic event		

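### Protocol Section 3.2 lists asymptomatic Grade 4 laboratory values and Hy's Law cases as DLTs, and the same paragraph lets the investigator waive them

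*Protocol*

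**What the plan says.** Protocol Section 3.2 states: "Dose-limiting toxicity is defined as any of the events listed in Table 4". The sentence that follows sets out what may be excused. It opens with "Toxicities with a clear alternative explanation (eg, due to disease progression) or transient toxicities", the latter defined as lasting 72 hours or less, and ends "abnormal laboratory values without associated clinically significant signs or symptoms based on investigator determination can be deemed a non-DLT".

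Table 4 comes next and sets its own conditions row by row. The row headed "Laboratory abnormality" counts Grade 3 persisting at least 7 days despite supportive care, or Grade 4. The AST/ALT row counts Grade 4 and every Hy's Law case. The infusion-reaction row counts a "Grade 4 infusion-related reaction that occurs during or within 24 hours after the infusion of JNJ-63723283 or daratumumab". The thrombocytopenia row reads, in part, "thrombocytopenia with clinically significant bleeding and Grade 4 thrombocytopenia lasting more than 7 days".

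The decision rule is in Section 3.1, Part 1: "If <2 of the first 6 DLT evaluable subjects experience a dose-limiting toxicity", the doses are considered tolerable and the study goes on to Part 2 once the SET approves. With 2 or more such subjects, run-in enrolment stops until the SET has met and made a recommendation.

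**The concern.** The definition and the waiver give different answers for the same event. A Grade 4 laboratory value without symptoms is a DLT by the table and can be declared not a DLT by the sentence above it. Nothing in Section 3.2 says which prevails.

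This matters for two reasons. Section 2.1 makes adverse events, including DLTs, the primary endpoint of Part 1, in what Section 1.4 calls the first study of this combination. The rule for moving to Part 2 also turns on a small count of subjects with a DLT. If investigators can remove Table 4 events from that count, a finding that the combination is tolerable does not mean what Table 4 suggests.

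**Working it through.** **Waiver against each Table 4 entry.** The documents state no operating characteristics for the run-in, so there is no plan figure to reproduce. The check is mainly one of wording.

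| Table 4 entry | Symptom condition in the row? | Within the laboratory waiver if asymptomatic? |
|---|---|---|
| AST/ALT Grade 4 | No | Yes |
| Hy's Law case | No | Yes |
| Laboratory abnormality, Grade 4, or Grade 3 for at least 7 days | No | Yes |
| Grade 4 neutropenia or anemia for more than 7 days | No | Yes |
| Grade 4 thrombocytopenia for more than 7 days | None in that limb | Yes |
| Febrile neutropenia, sepsis, bleeding | Clinical event | No |
| Grade 4 infusion reaction | Clinical event | No; at most through the 72-hour limb |

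Hy's Law is the clearest conflict. The footnote to Table 4 defines it by ALT or AST, bilirubin and ALP values alone and already rules out another cause. The table admits every such case, yet an asymptomatic one falls within the waiver.

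Where the authors wanted a symptom exception they wrote it into a row: the row for other non-hematologic events carves out mildly symptomatic or asymptomatic rash. Section 6.2.3 also requires study treatment to stop for Grade 3 or higher AST or ALT above 5 times the upper limit of normal. An event that ends treatment could thus be recorded as not dose-limiting.

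**Effect on the decision.** Section 3.1 counts subjects. If exactly two of six have Table 4 events, and one subject's only such event is waived, the count falls from 2 of 6 (enrolment pauses for the SET) to 1 of 6 (the rule is met).

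**Illustration, with assumed rates.** Let p be the true proportion of subjects with a Table 4 event and w the share of those subjects whose events are waived. Subjects are taken as independent. With q = p(1 − w),

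P(0 or 1 of 6) = (1 − q)^6 + 6q(1 − q)^5.

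For p = 0.40, w = 0: 0.6^6 + 6 × 0.4 × 0.6^5 = 0.0467 + 0.1866 = 0.233. For p = 0.40, w = 0.50, q = 0.20: 0.8^6 + 6 × 0.2 × 0.8^5 = 0.2621 + 0.3932 = 0.655.

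| p | w = 0 | w = 0.25 | w = 0.50 | w = 0.75 |
|---|---|---|---|---|
| 0.20 | 0.655 | 0.776 | 0.886 | 0.967 |
| 0.30 | 0.420 | 0.594 | 0.776 | 0.931 |
| 0.40 | 0.233 | 0.420 | 0.655 | 0.886 |
| 0.50 | 0.109 | 0.274 | 0.534 | 0.833 |

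Waiving can only raise the chance of meeting the rule. Neither p nor w is in the documents, so the table shows direction and range, not an estimate.

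**The case against.** The best defence is that the definition and its exception form one rule. The exception is permissive, and investigator judgement within a DLT definition is a legitimate choice. Passing is also not automatic. Section 3.1 requires SET approval, and Section 3.2 has the SET monitor all available treatment-emergent events, so a waived event stays in view. A separate SET charter, not available here, may cover adjudication. Section 10.2 allows termination on adverse events whatever the DLT count.

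Much of this stands: the run-in does not pass on a bare count. But the SET recommends on the basis of the same DLT rules, and its members include the enrolling investigators. An exception that reaches every laboratory row, with no statement that this is intended, still leaves the table's meaning open.

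The SAP is a further defence, since it lists all treatment-emergent events with grade, dates and a DLT flag, and gives laboratory shift tables. However, the mock listing LSFAE01 has one Y/N column for DLT, which cannot separate a waived event from one that never qualified. The shift tables cover worst grade during treatment, not Cycle 1. SAP Section 1.7 gives no DLT derivation; SAP Section 8 refers to a further document that is not available here.

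Two stronger readings are tempting but not established:

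- *Grade 4 infusion reactions can be waived.* The laboratory clause does not cover them. They are reached as transient toxicities only if the 72-hour limb stands alone. If the symptom qualifier also governs that limb, a life-threatening reaction would not fit. The grammar allows both readings, and the documents do not say how long such reactions last.
- *Thrombocytopenia needs both conditions at once.* The word *and* can be read that way, but a list of two events fits better. Table 4 is introduced as a list of events, any one of which counts. A joint requirement of Grade 4 would make the Grade 3 or higher threshold redundant. Section 6.1.5 lists thrombocytopenia with bleeding separately from Grade 4 hematologic toxicity.

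**Conclusion.** The inconsistency is real for the laboratory-defined entries: asymptomatic Grade 4 laboratory abnormalities, Grade 4 AST/ALT, Hy's Law cases and prolonged Grade 4 cytopenias. Two run-in subjects with Table 4 events could be counted as fewer than 2 with a DLT, subject to SET review. The scope of the 72-hour limb and the thrombocytopenia conjunction are lesser ambiguities.

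This rests on reading the laboratory clause as a separate category. If a laboratory value had to be both short-lived and asymptomatic, the prolonged cytopenias would fall outside the waiver. A Grade 4 AST or ALT resolving within 72 hours would still be both listed and waivable.

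A reader might infer that the run-in was passed improperly. The documents do not show that any event was waived, and they give no data from which to judge it.

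**What to change.** The sponsor should reconcile the waiver sentence with Table 4 and state three things: which rows the waiver reaches, whether the symptom qualifier also governs transient toxicities, and whether the two thrombocytopenia conditions are joint or separate. Which clinical rule is right is for the sponsor; this review does not choose one.

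Enrolment closed on 25 May 2018 and the combination was discontinued, so the useful change is in the SAP and study report:

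- List every run-in Cycle 1 event that meets a Table 4 criterion, from laboratory data as well as adverse event records.
- Mark each one deemed non-DLT, with the limb of the waiver used and the reason.
- Give the number of subjects with a DLT both before and after the waiver.

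The cost is a re-read of Cycle 1 data for about 6 subjects and a small addition to one listing. The downside is a possibly less favourable DLT count.

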#### Table 4: Criteria for Dose- limiting Toxicity

ALT=alanine aminotransferase, AST=aspartate aminotransferase, ALP=alkaline phosphatase; BSC=best supportive care

a. Toxicity graded according to the NCI-CTCAE, Version 4.03.

- b. Hy's Law criteria, defined as ALT or AST value  $\ge 3 \text{ x}$  upper limit of normal (ULN), total bilirubin  $\ge 2 \text{ x}$  ULN, and ALP  $\le 2 \text{ x}$  ULN; with no alternative etiology.
- c. Best supportive care (BSC) if available, according to institutional standards.

## Safety Evaluation Team (SET)

Ongoing safety evaluation during Part 1 and Part 2 will be overseen by the SET. The SET established by the Sponsor will monitor all available treatment-emergent adverse events on an ongoing basis. The SET will also be responsible for reviewing the safety data during the safety run-in phase and making a recommendation on whether the study will proceed to the 80-subject randomized phase (Part 2) based on the DLT rules set forth above.

The SET will be chaired by the Sponsor's Study Responsible Physician. Membership will include a Sponsor clinical scientist, safety physician, statistician, clinical pharmacologist, along with additional Sponsor staff, as appropriate. Additionally, the investigators who have enrolled the subjects in Part 1 and 2 will be members. The team will meet during the safety run-in phase and as necessary during the remainder of Part 1 and Part 2. Decisions with the potential to affect subject safety (eg, unfavorable change in benefit/risk assessment) will be promptly communicated to investigators and regulatory authorities as appropriate. Additional details will be specified in a separate SET charter.

# Independent Data Monitoring Committee (IDMC) – Part 3 (Phase 3)

In Part 3, ongoing safety evaluation will be performed by the IDMC. In addition, a formal safety review will be performed after 50 subjects have been treated for at least 8 weeks or discontinued the study treatment. The purpose of this safety review is to have a comprehensive evaluation of safety for the new drug product for JNJ-63723283 (see Section 14.1) in combination with daratumumab.

The IDMC, consisting of 2 clinicians and 1 statistician, will be established by the Sponsor to review efficacy and safety results at the pre-planned analyses. After the interim reviews, they will make recommendations regarding the continuation of the study. The details will be provided in a separate IDMC charter.

# 3.3. Study Design Rationale

# **Rationale for Study Design**

Adequate steps have been taken to ensure the validity of data in an open-label study design. This includes performing tumor assessments at the same frequency in both arms, adhering to protocoldefined schedules, and determining the strategy for the final analysis of the primary endpoint prior to study start, including predefined methods for handling missing data and censoring rules.

Randomization will be used to minimize bias in the assignment of subjects to treatment groups. To further minimize imbalance across treatment arms and to allow for balanced enrollment in important subgroup analyses, subjects will be stratified based on ISS staging and number of prior lines of therapy ( $\leq$ 3 prior lines vs. >3 prior lines).

# **Rationale for Daratumumab Dose Selection**

The daratumumab dose regimen used in this study (16 mg/kg) is approved in many regions as monotherapy and in combination with other therapies for the treatment of subjects with relapsed and refractory multiple myeloma. This dose regimen was selected based on an acceptable safety profile, maximal clinical activity, and pharmacokinetics consistent with saturation of the target. This dose and similar schedules have been shown to be tolerable in several combination studies.

# Rationale for JNJ-63723283 Monotherapy Dose Selection

As of May 2017, 17 subjects have been dosed with JNJ-63723283 monotherapy and completed DLT evaluation in the first-in-human study in patients with advanced solid tumors (Study 63723283LUC1001). This study continues to enroll subjects with various advanced solid tumor types and has expanded to Part 2, where subjects with selected tumor types are dosed at a recommended Phase 2 dose (RP2D) regimen of 240 mg every 2 weeks. The maximum dose regimen of JNJ-63723283 in the first-in-human study to date is 460 mg every 2 weeks; no maximum tolerated dose has been identified. To date, the safety profile of JNJ-63723283 is similar to the safety profile of other anti-PD-1 mAbs. Adverse events have been broadly consistent across tumor types following monotherapy and have not demonstrated a clear dose-response relationship (see Section 1.2.2 and the Investigator's Brochure for additional details).

The clinically efficacious dosing regimen for JNJ-63723283 is anticipated to be in the same range as similar anti-PD-1 mAbs. The approved dose regimens for these drugs include nivolumab 3 mg/kg or 240 mg every 2 weeks and pembrolizumab 2 mg/kg or 200 mg every 3 weeks (the body weights across nivolumab and pembrolizumab clinical studies have been reported as 79 kg [mean] and 77 kg [median], respectively, (Bajaj 2017; Freshwater 2017).

The RP2D regimen for JNJ-63723283 is 240 mg every 2 weeks in all tumor types based on the following:

- JNJ-63723283 demonstrated similar in vitro binding affinity to human PD-1 as pembrolizumab and nivolumab analogues (within 3-fold), similar potency in ex vivo mixed lymphocyte reaction and cytomegalovirus (CMV) assays as pembrolizumab and nivolumab analogues, and similar tumor growth inhibition in a MC38 mouse syngeneic model as a nivolumab analogue (see the Investigator's Brochure for additional details).
- Pharmacokinetic simulations based on preliminary modeling of observed clinical PK data through May 2017 (n=14, median body weight 75 kg) showed that following 240 mg IV JNJ-63723283 every 2 weeks, the predicted steady-state trough concentration, or  $C_{min,ss}$  of JNJ-63723283 (47 µg/mL) is expected to be similar to reported nivolumab  $C_{min,ss}$  at 3 mg/kg every 2 weeks (57 µg/mL) (CDER 2014) and approximately double the reported pembrolizumab  $C_{min,ss}$  at 2 mg/kg every 3 weeks (23 µg/mL) (CDER 2014).
- Preliminary PD-1 RO assessment on circulating CD3+ T cells following JNJ-63723283 dosing suggests dose-independent saturation from 80 to 460 mg, similar to the dose-independent clinical RO observed for nivolumab from 1 to 10 mg/kg (Topalian 2012).
- A semi-mechanistic translational PK/pharmacodynamics (PD) model was developed using PK, RO, and tumor growth inhibition data from MC38 syngeneic mouse studies as well as PK and RO data from healthy cynomolgus monkey studies. This translational PK/PD model suggested that IV doses ≥240 mg every 2 weeks in humans (corresponding to a predicted serum Cmin,ss of 42 µg/mL) would lead to maximum tumor killing effect in patients with non-small cell lung cancer (NSCLC). This prediction is consistent with the established clinically efficacious doses for nivolumab and pembrolizumab.
- Preliminary PK modeling of observed JNJ-63723283 clinical PK data through May 2017 projected a serum  $C_{min,ss}$  of 47 µg/mL following 240 mg every 2 week dosing, providing further evidence that the targeted JNJ-63723283 trough concentrations can be achieved at this dosing regimen.
- No clinically relevant impact of tumor type on drug exposure or clearance has been observed for nivolumab or pembrolizumab (Bajaj 2017; Ahamadi 2017).

